2.2 Secondary Objective(s)

To compare different surgical modalities (open procedures, minimally invasive procedures, and single-site technology) and different injectants (isosulfan blue and indocyanine green) for SLN biopsy.

To determine total operating room time (from the time the patient enters the room to the time the patient leaves the room) as well as console time (robotic)/ operating time for minimally invasive procedures.

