3.2 Number of Subjects

For this study, a sample size of 200 patients will initially be included. This sample size was calculated using the Raosoft sample size calculator online (available at <http://www.raosoft.com/samplesize.html>). A 5% margin of error was used, with a 95% confidence interval, a population size of 20,000 (as suggested), and a 15% response distribution. This 15% response distribution was chosen based on 2 large randomized trials that showed that the rates of positive pelvic lymph nodes in patients with presumed stage I-II disease were 9% and 13% respectively [36, 37]. In order to ensure an adequate sample size a 15% difference was utilized for this calculation.

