6.2 Intervention

Treatment must be administered only on an inpatient basis.

Patients who consent to participate in this study will be scheduled for their procedure in the normal fashion. Procedures will not be delayed for the purpose of the study. All procedures will be performed via the surgical modality determined by the surgeon.

On the day of surgery, after the patient has been placed under general anesthesia in the operating room, she will be placed in the dorsal lithotomy position, and she will undergo a routine examination under anesthesia. The patient will be prepped and draped in the usual sterile fashion.

Depending upon the surgical modality utilized, access the intra-abdominal cavity will be obtained (either via laparotomy or minimally invasive techniques). Subsequently, attention will be turned to the cervix, where a spinal needle will be used to inject 2ml of isosulfan blue directly into the cervix (1 ml at the 3 o'clock position and 1 ml at the 9 o'clock position) and/or ICG with 0.5 ml of ICG will be injected at both the 3 o'clock and 9 o'clock positions on the cervix. Following injection, the SLN will be identified and removed in a manner consistent with the algorithm proposed by Barlin et al (see Figure 1.), with sentinel lymph nodes removed from each hemi-pelvis [29]. After all mapped nodes are removed, they will be sent for pathologic examination via frozen section. Results of this analysis will be delivered to the surgeon via telephone call into the operating room. Subsequently, hysterectomy, bilateral salpingo-oophorectomy and a complete pelvic lymphadenectomy will be performed. All specimens removed will be sent to pathology. Para-aortic lymphadenectomy will be performed if the frozen section of the sentinel lymph node comes

back positive for metastasis. Otherwise, para-aortic lymphadenectomy will be performed at the discretion of the surgeon.

If, at any time, the surgeon determines that the above protocol is inappropriate, the procedure will be varied in the best interest of the patient.

The data that will be collected falls into three categories: demographic variables, procedural variables, SLN variables. The demographic variables will be collected at the time of the patient’s initial clinic visit. These variables will include: age, race, number of prior abdominal surgeries, and medical comorbidities.

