12.0 STATISTICAL CONSIDERATIONS

Numerical values will be summarized by mean and standard deviation when the data have an approximately normal distribution; otherwise they will be summarized by median and interquartile range. Normality will be evaluated through visual inspection of histograms, boxplots, and normal QQ plots. Analyses specific to each aim are listed below. Secondary multivariable analysis may include logistic regression using metastasis as the dependent variable with type of dy utilized, surgical modality, surgeon, tumor stage, grade and presence of lymphovascular space invasion as independent variables. Significance will be determined by a p-value less than or equal to 0.05 unless otherwise stated.

Specific Aim 1:

Sensitivity, specificity, and negative predictive value of SLN biopsy for detecting metastasis will be estimated and appropriate 95% confidence intervals for each value will be provided.

Specific Aim 2:

Sensitivity, specificity, and negative predictive value of SLN biopsy for detecting metastasis will be compared between surgical modalities using pairwise comparisons for each surgical modality. Comparisons will be performed using two sample tests of proportions based on a normal approximation. Since three such pairwise comparisons are required, significance will be determined by a Bonferonni adjusted significance level of $0.05 / 3 = 0.17$.

Specific Aim 3:

Sensitivity, specificity, and negative predictive value of SLN biopsy for detecting metastasis will be compared between injectants utilized using a two sample test of proportions based on a normal approximation.

Specific Aim 4:

Total operating room time will be estimated as a mean with 95% confidence interval if the data have an approximately normal distribution. Otherwise, the median and a bootstrapped 95% confidence interval for the median will be reported. Similar summaries will be provided for the console time (robotic)/ operating time.

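### Aim 2's Bonferroni level is printed as 0.17 and not 0.0167, and the planned normal-approximation tests are unreliable with few events; an exact overall test followed by exact pairwise tests at 0.05 mends both

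*Combined protocol and SAP*

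**What the plan says.** Section 2.2 makes the comparison of surgical modalities a secondary objective and names three groups: "open procedures, minimally invasive procedures, and single-site technology". Section 12.0, Specific Aim 2, compares sensitivity, specificity and negative predictive value (NPV) between each pair. On the test it says "Comparisons will be performed using two sample tests of proportions based on a normal approximation". On multiplicity it says "Since three such pairwise comparisons are required, significance will be determined by a Bonferonni adjusted significance level", and the level appears as "adjusted significance level of $0.05 / 3 = 0.17". The general rule earlier in that section is "Significance will be determined by a p-value less than or equal to 0.05 unless otherwise stated". No overall three-group test is planned and sidedness is not stated.

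No effect size, power or group size is given for this aim. Section 3.2 says "a sample size of 200 patients will initially be included", from a precision calculation for a single proportion: "A 5% margin of error was used, with a 95% confidence interval, a population size of 20,000 (as suggested), and a 15% response distribution". Group sizes are not controlled, since section 6.2 says "All procedures will be performed via the surgical modality determined by the surgeon".

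**The concern.** Three things in the Aim 2 sentence need attention together.

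- The printed level is ten times the quotient it is said to equal, and looser than the unadjusted 0.05. Applied literally, it would declare differences between modalities far too often.
- The pairwise tests rely on a normal approximation, although Aim 2 rests on few events. Sensitivity has perhaps 5 to 10 node-positive women per modality, and NPV has only a handful of false negatives. Surgeon's choice may also leave one or two modalities with small groups.
- If the tests are made exact and Bonferroni is kept, two conservative steps are stacked. With exactly three groups this is avoidable.

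At stake is whether a reported difference in sentinel node accuracy between modalities can be believed.

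**Working it through.** **1. The printed level.** 0.05/3 = 0.0167, so 0.17 does not reproduce; it is a tenfold slip.

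**2. Family-wise error under equality, three pairs, two-sided.**
- At 0.17: upper bound 3 × 0.17 = 0.51; if independent, 1 − 0.83³ = 0.43; allowing for shared groups (normal-theory simulation, equal groups), 0.356.
- At 0.0167: the same simulation gives 0.044.
- With sparse data the error at 0.17 is lower but still well above 0.05: 0.11 to 0.30 for sensitivity 93% with 5 to 10 women per group, and 0.20 to 0.26 for NPV 99% with 47 to 60 per group.

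**3. How much information Aim 2 has.**
- Size: 1.96² × 0.15 × 0.85 / 0.05² = 195.9 (194.0 with the finite-population correction), which supports 200 as a precision target only.
- Node-positive women with a detected node: from 200 × 0.09 × 0.78 = 14 to 200 × 0.15 × 1.00 = 30, so about 5 to 10 per modality if equal. The rates are from sections 3.2 and 1.3; 100% detection is the upper limit.
- Women with a negative sentinel node: 200 × 0.78 × (1 − 0.13 × 0.93) = 137 to 200 × 0.95 × (1 − 0.09 × 0.93) = 174.

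**4. The z test at 0.0167 when groups are unequal.** Assume 160 women with a negative node, split 15/130/15, and one false negative in a group of 15 against none in 130. The pooled rate is 1/145 and the standard error is √[(1/145)(144/145)(1/15 + 1/130)] = 0.0226. So z = 0.0667/0.0226 = 2.95 and p = 0.003: a single false negative is declared significant. Fisher's exact p is 15/145 = 0.10.

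If all three modalities have NPV 99%, the chance of no false negative in the 130 and at least one in the other 30 is 0.99¹³⁰ × (1 − 0.99³⁰) = 0.271 × 0.260 = 0.070. That pattern alone exceeds 0.05; adding the other rejecting tables gives about 0.08. A 20/120/20 split at NPV 98% also gives about 0.08. This is not a ceiling: with 20/120/20 at NPV 99%, one against none has z = 2.46, p = 0.014, and the pattern contributes 0.299 × 0.331 = 0.099.

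**5. Why the two-step procedure controls the error.** With three groups, if two of the pairwise equalities are true the third is too. The only intersection hypothesis is that all three are equal. Testing it at 0.05, and then each pair at 0.05, is therefore a closed procedure. With exact tests and a 10% failure rate in every group, its family-wise error is about 4.2% (60 each) and 4.7% (35/110/25); in the unequal sparse cases of step 4 it is lower. For 60 each, Fisher tests with Bonferroni give about 2.4% and z tests at 0.0167 give 4.4%.

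**6. Power.** Chance of at least one significant pair involving the one worse modality:

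| Assumed truth and group sizes | z at 0.0167 | Fisher at 0.0167 | Overall exact, then Fisher at 0.05 |
|---|---|---|---|
| NPV 99/99/92%, 60 each | 30% | 17% | 30% |
| NPV 99/99/90%, 60 each | 49% | 34% | 49% |
| NPV 99/99/90%, 35/110/25 | 53% | 30% | 53% |
| Sensitivity 95/95/60%, 8 each | 16% | 4% | 16% |

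Requiring both pairs with the worse group to be significant, the two-step procedure reaches about 16%, 30%, 17% and 10%.

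**7. One data pattern.** With 0, 0 and 6 false negatives in three groups of 60, the overall exact p is 0.0035 and two pairwise Fisher p values are 0.027. The two-step procedure declares a difference; Fisher with Bonferroni does not. The z test gives p = 0.012 and also declares it at 0.0167.

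**The case against.** A reader might infer that Bonferroni makes the plan too strict, so that large differences are missed which the two-step procedure would find. The documents do not support that. The only level printed is 0.17, which errs the other way. If 0.0167 is meant, the planned z tests already match the two-step exact procedure in all four scenarios. The gain appears only against Fisher tests with Bonferroni, which the plan does not propose.

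Other points against the change also have force.
- Bonferroni at 0.0167 is a valid, standard choice for a secondary comparison and gives simple simultaneous intervals. The two-step procedure does not, and it is not uniformly better: in large-sample simulation Bonferroni rejected a pair that the two-step test missed in up to about 0.6% of trials.
- The scenarios are extreme. With node positivity of 9 to 13% and specificity 100%, NPV 92% implies sensitivity of only about 12 to 42%; NPV 90% implies at most about 26% and is impossible at 9%. Table 2 reports NPV of 97 to 99%. Sixty negative women in each group (180 in all) is slightly above the 137 to 174 derived above.
- For realistic differences nothing helps: at NPV 99/99/97% the two-step procedure finds a difference in under 1% of trials, and within the cited 84 to 93% sensitivity range in at most 0.3%. Scarce events, not the multiplicity method, are the main limit.

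All of this stands as a limit on the claim. It does not rescue the printed 0.17, nor the z tests when groups are small and unequal.

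**Conclusion.** The point holds as a correction of error control, not as a gain in power over the plan. The printed 0.17 is wrong and would give a family-wise error of about 0.36 per measure in large samples. At 0.0167 the z tests are acceptable in balanced groups (4.4% with 60 each and a 10% failure rate), but reach about 8%, and more in one combination, when two modalities have 15 to 20 women and false negatives are rare. The two-step exact procedure stayed at or below 4.7% in the cases checked and is bounded by 5% in theory. It matches the power of the z tests at 0.0167 and exceeds that of Fisher tests with Bonferroni by about 12 to 23 percentage points in the four scenarios.

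These figures rest on two-sided tests and on assumed group sizes and rates, because the documents give none for Aim 2. The gain is for large differences only. Detection rate is not an Aim 2 measure, so no benefit is claimed for it. The bound applies to each measure separately: three measures by three pairs make nine tests, with no adjustment across measures. This is a minor improvement to a secondary aim, best made when the 0.17 is corrected, as it must be.

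**What to change.** In section 12.0, Specific Aim 2, replace the test and Bonferroni sentences with text to this effect: for each measure, the three modalities are compared by an overall Fisher-Freeman-Halton exact test at two-sided 0.05; only if it is significant is each pair compared by a two-sided Fisher exact test at 0.05; with three groups this keeps the family-wise error for the three pairs at or below 0.05 for that measure.

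Add that there is no adjustment across the three measures, that the comparison is exploratory, and that a significant overall test without a significant pair will be reported as a difference not attributed to any pair.

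The cost is a short edit and one extra test per measure, with no more patients or data. Simple simultaneous intervals are given up, so intervals for pairwise differences should be labelled unadjusted. If the sponsor prefers to keep Bonferroni, the least change is to print 0.0167 and use exact tests, accepting the lower power shown above.

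### The Bonferroni threshold for the three surgical-modality comparisons is printed as 0.17; 0.05/3 is 0.0167, and 0.17 is looser than no adjustment

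*Combined protocol and SAP*

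**What the plan says.** Section 12.0 opens with a default rule: "Significance will be determined by a p-value less than or equal to 0.05 unless otherwise stated". Specific Aim 2 then departs from it for the comparison of sensitivity, specificity and negative predictive value (NPV) between surgical modalities. The tests are described as follows: "Comparisons will be performed using two sample tests of proportions based on a normal approximation". The reason for adjusting is given as "Since three such pairwise comparisons are required", and the rule that follows is that "significance will be determined by a Bonferonni adjusted significance level of $0.05 / 3 = 0.17".

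The count of three matches Section 2.2, which names three modality groups: open, minimally invasive and single-site. No other section gives a threshold for this comparison.

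**The concern.** A Bonferroni adjustment divides the significance level by the number of tests, so its result can never exceed the level it started from. Here the result is larger than 0.05. Because the default applies only where nothing else is stated, and Aim 2 states something else, an analyst who takes the printed number at face value would test each pair at 0.17.

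What is at stake is the only between-modality test of accuracy that the plan specifies, which serves a named secondary objective. Under Section 6.2 the surgeon chooses the modality, so the comparison is already open to confounding. A lax threshold would add chance findings to that. It also leaves the analyst in a bind: using 0.17 follows the text and inflates error, while using 0.0167 departs from the printed number.

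**Working it through.** **Inputs**
- Unadjusted level: 0.05 (Section 12.0, opening paragraph).
- Number of comparisons: 3 (Section 12.0, Specific Aim 2; three modality groups in Section 2.2 give 3 pairs).
- Printed adjusted level: 0.17 (Section 12.0, Specific Aim 2).
- Sidedness is not stated; two-sided tests are assumed below.

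**Step 1. Try to reproduce 0.17**
- Bonferroni: 0.05 / 3 = 0.016667. This does not give 0.17.
- Sidak: 1 − 0.95^(1/3) = 0.01695. No.
- Starting from 0.10: 0.10 / 3 = 0.0333. No.
- Multiplying instead of dividing: 0.05 × 3 = 0.15. No.
- Only 0.5 / 3 = 0.1667 rounds to 0.17, which points to a decimal slip.

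**Step 2. Size of the error**
- Against the correct value: 0.17 / 0.016667 = 10.2.
- Against the unadjusted default: 0.17 / 0.05 = 3.4.

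**Step 3. Family-wise error for three tests of one accuracy measure**

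The upper bound is 3 × α. If the tests were independent, the rate would be 1 − (1 − α)³. Pairwise tests among three groups share data and are correlated, so the last column uses the distribution of the largest of three pairwise z-statistics with equal groups (simulation, confirmed by the studentized range distribution).

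| Level per test | Critical \|z\| | Bound | If independent | All pairs, equal groups |
|---|---|---|---|---|
| 0.17 (as printed) | 1.37 | 0.51 | 0.428 | 0.356 |
| 0.05 (no adjustment) | 1.96 | 0.15 | 0.143 | 0.122 |
| 0.0167 (0.05/3) | 2.39 | 0.05 | 0.049 | 0.044 |

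The documents give no modality split. With an assumed 2:7:1 split the last column becomes 0.346, 0.118 and 0.042, so the result depends little on group balance.

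**Step 4. Check at the sample sizes this trial could have**

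Section 3.2 plans 200 patients and cites node-positive rates of 9% and 13%, with 15% used for planning. That gives 200 × 0.09 = 18 to 200 × 0.15 = 30 node-positive patients before detection failures, or about 6 to 10 per modality if split evenly. The table shows the family-wise error of the pooled two-proportion z-test with equal true values in all groups. Group sizes of 7 (sensitivity) and 52 (NPV) are assumed; the true values are taken from Section 1.3.

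| Measure, true value, size per group | At 0.17 | At 0.05 |
|---|---|---|
| Sensitivity 93%, 7 | about 19% | about 0.2% |
| Sensitivity 84%, 7 | about 40% | about 2.5% |
| NPV 99%, 52 | about 22% | about 0.5% |
| NPV 97%, 52 | about 47% | about 8% |

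In these cells the normal approximation is poor and the absolute rates move a good deal, but 0.17 is far looser than 0.05 in every one.

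**The case against.** The strongest reply is that this is an obvious slip. The sentence names the method, gives the number of comparisons and prints the division; only the result is wrong, and an analyst who evaluates 0.05/3 gets the right threshold. That is fair as to intent. It makes the correction uncontroversial, but the plan still prints a wrong decision threshold in the one place where it sets one.

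A second reply is that the aim is secondary, in a non-randomised cohort, and that neither the Aim 1 estimates nor the sample size uses this number. That is correct and limits how much harm the error can do. It does not make the number right.

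A third reply is that the 36%, 12% and 4.4% figures are generic. This stands in part. They are large-sample rates for two-sided tests and equal groups, not this trial's own error rates, as the small-sample check shows. They also do not apply to specificity. Under Section 10.1.1 the only error defined is a false negative, and a positive sentinel node is itself nodal metastasis, so specificity is 100% in every group and its test cannot reject at any threshold. For sensitivity and NPV, which can vary, the direction is unchanged.

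Finally, a digit lost in PDF reading cannot be fully excluded. Nothing in the text suggests it, and a look at the source file would settle it.

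**Conclusion.** The concern holds. The adjusted level for Specific Aim 2 is wrong as written: 0.17 where the plan's own expression gives 0.0167. Applied literally, the rule does the opposite of its purpose, raising the family-wise false-positive rate for one accuracy measure from about 12% with no adjustment to about 36%, instead of lowering it to about 4.4%. Those three rates assume large samples, two-sided tests and three equal groups, and should be read as illustrations. The arithmetic error, and the fact that 0.17 exceeds the default of 0.05, rest on no assumptions. The effect is confined to the modality comparison.

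**What to change.** In Section 12.0, Specific Aim 2, change the printed result of 0.05/3 from 0.17 to 0.0167, and state that it applies to each of the three pairwise modality comparisons. Three decimals or more are needed; 0.0167 is preferable to 0.017, since 3 × 0.017 = 0.051 slightly exceeds 0.05.

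The cost is one number. Design, data collection and sample size do not change. Fewer comparisons will be called significant than under 0.17, as the plan intends. The correction should be made before the modality comparison is analysed.

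A separate question, which this correction does not settle, is whether dividing by 3 is enough when three accuracy measures are each compared across three pairs. That makes nine tests: the bound at 0.0167 each is 9 × 0.0167 = 0.15, and covering all nine would need 0.05/9 = 0.0056.

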This meta-analysis reported a detection rate of 78% and a sensitivity of 93% for sentinel lymph node biopsy. From this study, assuming a 10% metastasis risk, a false negative rate of 1% was calculated [18].

Since the publication of this meta-analysis, there have been four additional prospective studies on SLN biopsy in endometrial cancer that these authors were able to identify. Examining the results from these 4 prospective trials, sensitivity of SLN biopsy is high, and negative predictive value (NPV) is also relatively high (Table 2.).

Table 2. Results from recent prospective studies

Author	Year	Type	Pts	Detection	Inj	Procedure	Detection	Sens	NPV
How	2012	Prospective	100	Isotope	C	Robotic	92%	89%	99%
Solima	2012	Prospective	59	Isotope	H	Ex-lap or LSC	95%	90%	98%
Buda	2012	Prospective	25	Isotope/ISB	C	Ex-lap or LSC	91%	100%	Unk
Ballester	2011	Prospective	125	Isotope/ISB	C	Ex-lap or LSC	89%	84%	97%

While the evidence that exists is encouraging, it is important to recognize that we are still in the early stages of analysis of SLN biopsy in endometrial cancer. The number of patients studied thus far does not yet allow us to get an accurate sense of the true false-negative rate [3], and large, prospective, randomized controlled trials will be necessary to validate these findings.

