1.4.4 Surgical Modality and Sentinel Lymph Node Biopsy

To our knowledge, thus far, sentinel lymph node biopsy procedures have been performed by laparotomy, conventional laparoscopy, and conventional robotics. Evidence suggests that minimally invasive techniques, including laparoscopy and robotics, should now be the standard of care for endometrial cancer [30], however, at times, open procedures may also be

necessary. Single-port laparoscopy is also now being utilized for endometrial cancer cases [31], yet, to our knowledge, there are no reports of single-port technology utilized for sentinel lymph node biopsy. While there is still limited prospective data on the benefits of single-port techniques, the available data suggests that outcomes for single-port laparoscopy are similar to those of conventional laparoscopy, with the added benefit of improved cosmesis and decreased pain [32].

The most recent advance in single-port technology is the single-port robot, which is now FDA-approved for gynecologic cases [33]. Robotic technology has provided improved optics, improved range of motion, and a shorter learning curve when compared to conventional laparoscopy [34]. A recent study by Escobar et al. compared LESS surgery to conventional LSC and robotic surgery for endometrial cancer and found no difference in outcomes [35]. In a recent study by Rossi et al, the robot was utilized to perform SLN biopsy in both endometrial and cervical cancers. The findings in this study suggest that robotics might have additional advantages specific for SLN biopsy procedure. This study showed a relatively short operating room time (186 min from patient entry into the room until exiting the room), as well as the ability to utilize new and integrated technologies (a fluorescence imager) [28]. These advantages will also translate to single-port robotics as technology develops [31].

1.5. **Rationale**

By performing sentinel lymph node biopsy for endometrial cancer, we may be able to further minimize the risks of lymph node evaluation, while continuing to obtain critical prognostic information for patients. In this study, we examine detection rates, false negative rates, and negative predictive value of SLN biopsy for endometrial cancer in order to further add to the body of evidence on SLN biopsy for endometrial cancer.

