10.1.1 Definitions

Sensitivity, false negative and false negative rate will be limited to those patients in whom a sentinel node is detected.

False negative = a sentinel node that is identified and determined to be negative, however, upon complete lymphadenectomy, a different lymph node is found to be positive

Sensitivity = the number of patients with a positive SLN over those patients with a positive SLN plus those patients with a false negative lymph node

False negative rate = 1-sensitivity or the number of patients with a false negative SLN over the number of patients with a positive SLN plus those with a false negative lymph node

	Our definition	Other definition
FN	H	F+H
FN Rate	$H/D+H$	$F+H/D+F+H$
Sensitivity	$D/D+H$	$D/D+F+H$
NPV	I/E	-

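### Aims 2 and 3 apply normal-approximation tests to about 1 to 4.6 expected false negatives, and Aim 3 has no rule for patients given both dyes

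*Combined protocol and SAP*

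**What the plan says.** Section 12.0 compares sensitivity, specificity and NPV between three surgical modalities, pairwise (Aim 2): "Comparisons will be performed using two sample tests of proportions based on a normal approximation". For Aim 3 the same measures are "compared between injectants utilized using a two sample test of proportions based on a normal approximation". It gives no exact alternative and no minimum count, and it does not say whether the variance is pooled. For Aim 2, "significance will be determined by a Bonferonni adjusted significance level of $0.05 / 3 = 0.17"; since 0.05/3 = 0.0167, the printed value is a separate error.

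Section 10.1.1 narrows the denominator: "Sensitivity, false negative and false negative rate will be limited to those patients in whom a sentinel node is detected". On size, Section 3.2 states that "a sample size of 200 patients will initially be included", calculated from the precision of one proportion in all patients. No power, effect size or group size is given for Aims 2 and 3.

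Section 6.2 leaves the surgical modality to the surgeon. It allows isosulfan blue, ICG, or both in one patient. It records SLN counts by dye, but lists positive nodes without the dye that found them.

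**The concern.** Sensitivity and NPV both fail only through false negatives. If the whole study produces a handful, a z-test on subgroups of that handful has no reliable reference distribution. Depending on the split, it may almost never reject, may be 0/0, or may reject on a single patient. These are the planned tests for the Section 2.2 comparison of modalities and injectants, so a modality or dye could be reported as worse because of one missed node.

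The both-dye gap is separate. A two-sample test assumes independent groups, and a patient counted under both dyes breaks that. If the dye behind each positive SLN is not recorded, per-dye sensitivity may not be recoverable later.

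**Working it through.** **The plan's own figure.** With x = 1.96² × 0.15 × 0.85 = 0.4898, n = 20,000x / (19,999 × 0.05² + x) = 194.0, rounded up to 195. The stated 200 is reproduced to within 3%. It concerns one proportion in all patients, not these comparisons.

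**Inputs.**
- Node-positive rate: "rates of positive pelvic lymph nodes in patients with presumed stage I-II disease were 9% and 13% respectively" (Section 3.2), with 15% used there for planning.
- Detection: 78% (meta-analysis) up to 95% (Section 1.3, Table 2).
- Sensitivity: "This meta-analysis reported a detection rate of 78% and a sensitivity of 93% for sentinel lymph node biopsy" for the upper planning value, and 84% from the lowest study in Table 2. One 25-patient study in that table reports 100%.

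**Expected counts.** Mapped node-positive patients = 200 × prevalence × detection:
- low: 200 × 0.09 × 0.78 = 14.0
- middle: 200 × 0.13 × 0.89 = 23.1 (24 used below)
- high: 200 × 0.15 × 0.95 = 28.5

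False negatives = that count × (1 − sensitivity): 14.04 × 0.07 = 0.98 up to 28.5 × 0.16 = 4.56. Even at the top, two equal groups expect 2.3 each and three expect 1.5.

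**True size of the z-test.** This is a full enumeration of both binomials, two-sided, with 0/0 counted as no rejection. All splits are assumptions. For Aim 2 the intended level is taken as 0.0167.

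| Comparison | Level | True rate | Pooled | Unpooled | Fisher |
|---|---|---|---|---|---|
| Sensitivity, 12 vs 12 | 0.05 | 93% | 0.006 | 0.040 | 0.001 |
| | | 84% | 0.032 | 0.092 | 0.008 |
| Sensitivity, 4 vs 20 | 0.05 | 93% | 0.069 | 0.043 | 0.007 |
| | | 84% | 0.039 | 0.216 | 0.012 |
| Sensitivity, 8 vs 8 | 0.0167 | 93% | 0.0001 | 0.0015 | <0.0001 |
| | | 84% | 0.002 | 0.016 | 0.0002 |
| Sensitivity, 3 vs 17 | 0.0167 | 93% | 0.062 | 0.008 | 0.004 |
| | | 84% | 0.035 | 0.080 | 0.005 |
| NPV, 78 vs 78 | 0.05 | 99.0% | 0.008 | 0.008 | 0.0001 |
| | | 97.7% | 0.036 | 0.036 | 0.003 |
| NPV, 30 vs 126 | 0.05 | 99.0% | 0.087 | 0.031 | 0.013 |
| | | 97.7% | 0.060 | 0.168 | 0.022 |

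The NPV rows use 200 × 0.89 = 178 mapped patients, 13% node-positive: 1 − NPV = 1.62/156.5 = 0.0104 at 93% sensitivity and 3.70/158.6 = 0.0233 at 84%. About 156 SLN-negative patients are used for both. The letter key to the table in Section 10.1.1 is not shown; I read H as false negatives and E as SLN-negative patients.

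Chance of 0/0 with 24 patients: 0.93²⁴ = 0.175 (84%: 0.015).

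**One false negative.** If it falls in the smaller group (n1 of N = n1 + n2), pooled z² = (n2/n1) × N/(N − 1), and Fisher's two-sided p = n1/N.
- 2/3 vs 17/17: z² = (17/3)(20/19) = 5.965, p = 0.015; Fisher 3/20 = 0.15.
- 3/4 vs 20/20: z² = (20/4)(24/23) = 5.217, p = 0.022; Fisher 4/24 = 0.17.

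The first passes 0.0167; the second passes only 0.05, the Aim 3 level.

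**The case against.** The strongest reply is that the pooled z-test is usually conservative here, that power and not the approximation is the main limit, and that the aims are secondary. Much of this stands. Balanced groups with pooled variance do not generate false claims, and the largest sizes (0.216, 0.168) need the unpooled variance, which Section 12.0 neither specifies nor excludes. The pooled excesses shown all need splits of about 1:4 or wider. An exact test does not restore power.

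Three stronger readings are tempting but not supported:
- A reader might infer that the dye groups will be lopsided too. The text supports imbalance only for modality: Section 1.4.4 holds that "minimally invasive techniques, including laparoscopy and robotics, should now be the standard of care for endometrial cancer", with open surgery at times necessary, and the surgeon chooses. Nothing indicates the dye split, so the 4 vs 20 example is only an assumption for Aim 3.
- A reader might take 1 to 4.6 as a firm forecast. It depends on rates for presumed stage I-II disease, while the eligibility criteria set no stage limit, and the 15% is a planning allowance, not an observed rate. At an assumed prevalence of 20 to 25%, with 89% detection and 84% sensitivity, the total is 5.7 to 7.1 (200 × 0.89 × 0.20 × 0.16 and × 0.25 × 0.16). That is still sparse per group. The study with 100% sensitivity would lower the count.
- A reader might conclude that the specificity comparison is void. That follows only if final pathology sets SLN status, so that every positive SLN is a true positive. Section 6.2 also uses frozen section, and a figure in Section 10 is not shown.

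**Conclusion.** The point holds for the tests of sensitivity and NPV in Aims 2 and 3. On the protocol's planning rates, the false negatives are too few for a normal approximation. The direction of the error depends on group balance and on an unstated variance choice. Pooled and balanced, the test is mainly conservative, or undefined in 18% of studies (24 patients, 93% sensitivity). Pooled and lopsided, it can exceed its level, and a single false negative can decide the result. It does not follow that these tests generally inflate type I error. All sizes rest on assumed splits, and the Aim 2 figures also on 0.0167 as the intended level.

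The both-dye gap needs no assumption about splits: both dyes are permitted, and no rule places such a patient in Aim 3. The primary estimates in Aim 1 are not affected. The change should be made, but nothing primary depends on it.

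**What to change.** (a) In Aims 2 and 3, replace the z-tests for sensitivity and NPV with Fisher's exact test, two-sided, and give exact 95% confidence intervals for each group. Label the comparisons descriptive. State whether SLN status is set by final pathology. If it is, and every positive SLN is therefore a true positive, report specificity as 100% by construction and do not test it.

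(b) In Aim 3, classify each patient once as blue only, ICG only or both. Compare blue only with ICG only. Within both-dye patients, report per-dye results with paired methods, for example a cross-table of positive SLN, negative SLN and not mapped for each dye, keeping patients mapped by one dye alone. Record the dye for each positive SLN.

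Cost: SAP wording and one data field. Power falls: for an illustrative 93% vs 70% sensitivity at 12 vs 12 and level 0.05, Fisher has 13% and the pooled z 26%. If half of 24 patients received both dyes (assumed), blue only vs ICG only at 6 vs 6 leaves Fisher 1%. The intervals then carry the information, and they are wide: 11/12 gives 62% to 99.8%, and 7/8 gives 47% to 99.7%.
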